### **3.1 Sample Size**

45 postmenopausal women with the diagnosis of metastatic breast cancer will be enrolled into the study

### **3.2 Study Population**

### **3.2.1 Inclusion criteria**

1. Postmenopausal women able to comply with the protocol requirements with metastatic breast cancer, whose tumors are estrogen (ER) and/or progesterone (PgR) positive, defined by core biopsy immunohistochemistry with > 10% positive malignant epithelial cells.
2. Patients must have documented expression of either PDGFR or CD117 (c-kit) by immunohistochemistry.
3. Patients may have received tamoxifen in the adjuvant/neoadjuvant setting. Patients may have previously received chemotherapy in the adjuvant/ neoadjuvant setting, though this is not required. Prior chemotherapy for metastatic breast cancer is allowed. Concomitant bisphosphonates are allowed for patients with bone metastases and who have another site of measurable disease.
4. Post menopausal status defined by one of the following :
  - no spontaneous menses for at least 1 year, in women >55 years
  - spontaneous menses within the past 1 year in women ≤ 55 years with postmenopausal gonadotrophin levels (LH and FSH levels >40 IU/L ) or postmenopausal estradiol levels ( <5 ng/dl) or according to the definition of “postmenopausal range” for the laboratory involved
  - bilateral oophorectomy
5. Performance status, ECOG ≤ 2
6. Patients must have measurable disease, defined as at least one lesion that can be accurately measured in at least one dimension (longest diameter to be recorded) as ≥10 mm with conventional techniques. See section 8.2 for the evaluation of measurable disease. Bone disease only will not be accepted as measurable disease. Pleural or peritoneal effusions will not be accepted as measurable disease.
7. Adequate bone marrow function (ANC  $\geq 1.5 \times 10^9/L$  and platelets  $\geq 100.0 \times 10^9/L$ , and hemoglobin  $> 10.0 \text{ g/dL}$ ).
8. Adequate renal function (creatinine less than 1.5 mg/dl) and hepatic function (T. Bilirubin less than 1.5 x normal, AST less than 2.5 x normal)
9. A life expectancy of at least 6 months
10. Localized radiotherapy, which does not influence the signal of evaluable lesion, is allowed prior to the initiation of Imatinib Mesylate. Patients must have recovered from the myelosuppressive effects of previous radiotherapy (at least 2-4 weeks).
11. Ability to understand and the willingness to sign a written informed consent.

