#### 2.2 Letrozole

Letrozole molecular weight is 285.31. It is freely soluble in dichloromethane, slightly soluble in ethanol, and practically insoluble in water. In human liver microsomes, letrozole strongly inhibits the cytochrome P450 (CYP) isoenzyme 2A6 (CYP 2A6) and moderately inhibits the CYP isoenzyme 2C19 (CYP 2C19). Letrozole has not been shown to affect synthesis of adrenal corticosteroids, aldosterone, or thyroid hormones. Rapidly and completely absorbed. Absorption is not affected by food. The volume of distribution (Vol D) is approximately 1.9 liters per kg of body weight. It is biotransformed in the liver, by the CYP isoenzymes 3A4 and 2A6 (CYP 3A4 and CYP 2A6), to an inactive carbinol metabolite and its ketone analog. Its half life is approximately 2 days. Time to steady-state concentration in the plasma is 2 to 6 weeks. Letrozole is eliminated renally, approximately 90% of a dose (approximately 75% as the glucuronide conjugate of the inactive metabolite, 9% as two unidentified metabolites, and 6% unchanged). Letrozole does not go under any metabolism through the CYP450.

Letrozole (4,4'-(1H-1,2,4-Triazol-1-ylmethylene)bis-benzonitrile) is a synthetic achiral benzyltriazole derivative. It is an orally active highly selective non-steroidal competitive inhibitor of the aromatase enzyme system. Aromatase inhibitors block the aromatase enzyme, consequently lowering estrogen

levels and thereby deprive the tumor of its growth stimulus. Letrozole effectively inhibits the conversion of androgens to estrogens in both *in vitro* and *in vivo*. This property makes it in particular suitable for postmenopausal women whose main source of estrogen is via peripheral aromatization of androgen precursors.

Letrozole is up to 150-250 times more potent than the first generation aromatase inhibitor Aminoglutethimide (AG), *in vitro* and more than 10,000 times as potent as AG in inhibiting aromatase *in vivo*. The high potency of Letrozole is not accompanied by any significant effect on adrenal steroidogenesis *in vitro* or *in vivo* over its maximally effective dose range. Inhibition of adrenal steroidogenesis resulting in adrenal hypertrophy does occur with therapeutic doses of AG. The high potency and selectivity of Letrozole explains its pharmacological profile and high therapeutic index.

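### Inclusion item 4 is inconsistent for women aged 55 or under with intact ovaries: recent menses plus postmenopausal hormone levels qualifies, but over a year of amenorrhoea with the same levels does not

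*Combined protocol and SAP*

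**What the plan says.** All references are to the combined protocol and SAP.

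Section 3.2.1, item 1 restricts entry to "Postmenopausal women able to comply with the protocol requirements with metastatic breast cancer". Sections 3.0 and 3.1 also describe the patients as postmenopausal. Item 4 says what that term means: "Post menopausal status defined by one of the following". Three bullets follow, and any one is enough.

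- **Bullet 1:** "no spontaneous menses for at least 1 year, in women >55 years". No hormone test is attached.
- **Bullet 2:** "spontaneous menses within the past 1 year in women ≤ 55 years with postmenopausal gonadotrophin levels" (LH and FSH above 40 IU/L), "or postmenopausal estradiol levels ( <5 ng/dl) or according to the definition of" the laboratory's postmenopausal range. The menses condition is "spontaneous menses within the past 1 year in women" of that age, with no negative in front of it.
- **Bullet 3:** "bilateral oophorectomy", with no condition on age or menses.

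Section 2.2 gives the pharmacological reason for the restriction. After describing aromatase inhibition by letrozole, it says: "This property makes it in particular suitable for postmenopausal women whose main source of estrogen is via peripheral aromatization of androgen precursors".

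**The concern.** Bullet 1 asks for the absence of menses, and bullet 2 asks for their presence. Between them, a younger woman with intact ovaries and a long amenorrhoea has no way in, although she is closer to the stated population than the woman whom bullet 2 admits.

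Screening staff apply eligibility text literally. As it stands, they would turn away women whom the trial appears to want and accept others whose menopausal status rests on a hormone result alone. It would also be unclear which entries count as protocol violations. The trial has a single arm, and section 13.0 judges its response rate against letrozole alone, using a trial that section 2.2.1 describes as enrolling postmenopausal women. The definition of postmenopausal therefore bears on how like the reference population the enrolled patients are.

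**Working it through.** The plan gives no figure on this point, so there is none to reproduce. The check is logical: list every combination of the four facts that item 4 uses and see which qualify.

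**Inputs, all from section 3.2.1, item 4**

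- Age: over 55, or 55 or under.
- Spontaneous menses within the past year: yes or no. 'No' is treated as at least one year without menses.
- Hormone condition of bullet 2: met or not. It is met if LH and FSH are both above 40 IU/L, or estradiol is below 5 ng/dl, or the laboratory's postmenopausal range applies.
- Bilateral oophorectomy: yes or no.

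This gives 2 × 2 × 2 × 2 = 16 combinations.

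**Rule as written:** eligible if (over 55 and no menses in the year), or (55 or under and menses in the year and hormone condition met), or oophorectomy.

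**Two possible corrections, for comparison**

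- A: insert 'no' at the start of bullet 2.
- B: keep bullet 2 and add a route for women aged 55 or under with no menses in the year and the hormone condition met.

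The 8 combinations with oophorectomy are eligible under every version. The other 8 are:

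| Age | Menses in past year | Hormone condition | As written | A | B |
|---|---|---|---|---|---|
| >55 | yes | met | not eligible | not eligible | not eligible |
| >55 | yes | not met | not eligible | not eligible | not eligible |
| >55 | no | met | eligible | eligible | eligible |
| >55 | no | not met | eligible | eligible | eligible |
| ≤55 | yes | met | **eligible** | not eligible | eligible |
| ≤55 | yes | not met | not eligible | not eligible | not eligible |
| ≤55 | no | met | **not eligible** | eligible | eligible |
| ≤55 | no | not met | not eligible | not eligible | not eligible |

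**Results**

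- Correction A changes 2 of 16 combinations and leaves 14 unchanged. Correction B changes 1 and leaves 15. Every change is in women aged 55 or under without oophorectomy.
- With the hormone condition met and ovaries intact, recent menses are required of a woman of 50 and disqualify a woman of 56.
- A woman of 50 with two years of amenorrhoea is refused whatever her hormone levels. If she stays amenorrhoeic, she qualifies on turning 56 with no hormone test.
- The row for women aged 55 or under with amenorrhoea and the hormone condition met is wrong as written whichever correction is chosen.

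These are counts of combinations, not of patients. They show where the rule misfires, not how often.

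**The case against.** The best defence is that bullet 2 may be deliberate: where menses were recent, the protocol asks for hormonal proof of menopause. Menses within the past year also covers a last period eleven months ago, so the wording need not describe a woman who is still cycling. This reading cannot be excluded. It explains why bullet 2 admits whom it admits, but not why amenorrhoeic women of the same age with the same hormone levels have no bullet. It also leaves the clash with bullet 1.

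A second defence is that item 1 and sections 3.0 and 3.1 already require postmenopausal women. They make the intention plain, but they do not repair the rule, because item 4 defines the word they use.

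A reader might infer more than the documents support, in four ways:

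- **Recent menses alone qualifies a younger woman.** It does not, because the hormone condition in the same bullet must also be met. That condition is fairly loose, since its alternatives are joined by 'or', but the gonadotrophin route needs both LH and FSH.
- **The trial selects the wrong population.** Women over 55 are classified consistently with the stated population, and so are women with oophorectomy.
- **A 'no' was certainly dropped.** This is plausible given bullet 1, but it remains an inference.
- **The response rate would be diluted by a stated amount.** Section 2.2 calls letrozole particularly suitable for postmenopausal women. It does not say that women with recent menses and postmenopausal hormone levels fail to respond, and the documents give no age or menopausal mix.

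**Conclusion.** The point holds as an inconsistency in the eligibility definition, confined to women aged 55 or under without bilateral oophorectomy. For them, bullet 2 admits recent menses with postmenopausal hormone levels and leaves out longer amenorrhoea with the same levels. It is more than a clerical matter, because literal application changes who may enter.

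The conclusion rests on item 4 being applied as written and on its three bullets being the whole definition, which is how the item is framed. It does not depend on whether a word is missing, since the gap for amenorrhoeic younger women exists under either reading of bullet 2.

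Its size in patients is unknown. The documents do not report how many candidates fall in this subgroup, so no number of the 45 places, loss of accrual or shift in objective response rate can be derived, and none should be quoted.

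**What to change.** Amend item 4 before enrolment so that its bullets agree with each other and with the population stated in item 1 and sections 3.0 and 3.1.

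1. The investigator checks the source text and confirms whether women aged 55 or under with menses in the past year and postmenopausal hormone levels are meant to be eligible. Bullet 2 is then reworded, or kept and labelled as a deliberate hormone-confirmed route.
2. In either case, item 4 gains a qualifying route for women aged 55 or under with at least one year of amenorrhoea, using the hormone tests already listed. If the answer to step 1 is that a 'no' is missing, restoring it provides this route.
3. The revised bullets are checked against the table above so that no intended group is left without a route.

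The cost is a short eligibility amendment with the approvals that section 12.1 requires. It adds no tests beyond those already named in bullet 2, and it leaves the sample size and the stopping rules as they are.

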### **3.2.2. Exclusion Criteria**

1. Prior treatment with Letrozole or Imatinib Mesylate.
2. Uncontrolled endocrine disorders such as diabetes mellitus, confirmed hypo- or hyperthyroidism, Cushing's Syndrome, Addison's disease (treated or untreated).
3. Patients with unstable angina, or uncontrolled cardiac disease (e.g. Class III or IV New York Heart Association's Functional Classification).
4. Other concurrent malignant disease with the exception of cone-biopsied *in situ* carcinoma of the cervix uteri, or adequately treated basal or squamous cell carcinoma of the skin, or other curable cancers e.g. Hodgkin's disease or NHL, provided 5 years have elapsed from completion of therapy, and there has been no recurrence.

5. Concomitant treatment with steroids, e.g. glucocorticoids for indications other than cancer, except aerosol for obstructive airways diseases and steroid injection to the joints for treatment of inflammation.
6. Other investigational drugs within the past 3 weeks and the concomitant use of investigational drugs.
7. History of non-compliance to medical regimens and patients who are considered potentially unreliable.
8. Patients with known brain metastasis.
9. Patients with known chronic liver disease (i.e., chronic active hepatitis, and cirrhosis).
10. Patients with known diagnosis of human immunodeficiency virus (HIV) infection.
11. Patients who received chemotherapy within 4 weeks (6 weeks for nitrosourea or mitomycin-C) prior to study entry, unless the disease is rapidly progressing.
12. Patients who previously received radiotherapy to  $\geq 25\%$  of the bone marrow.
13. Patients who had a major surgery within 2 weeks prior to study entry.

## **4.0 Study Drug Information**

### **4.1 Letrozole (Femara, Novartis)**

Letrozole is commercially available as 2.5 mg tablets and is supplied in bottles of 30 tablets each. Letrozole is stored at 25 °C.

### **4.2 Imatinib Mesylate (Gleevec, Novartis)**

Novartis will supply Imatinib Mesylate (ST1571) as 100 mg tablets packaged in bottles for an exposure period of up to 12 months or so long as the patient remains on study provided the patient shows continuous benefit from treatment with Imatinib Mesylate and there are no safety concerns. Continuing treatment beyond this period will be at the discretion of the investigator and may become the financial responsibility of the patient if no alternative method of obtaining or paying for the drug can be identified at that time. Medication labels will comply with the legal requirements of the US and will be printed in English. The storage conditions for Imatinib Mesylate will be described on the medication label. Bottles must be stored in a safe, secure location.

## **5.0 Treatment Plan**

### **5.1 Phase I Part**

The first 3 patients will be started at a dose of 300 mg Imatinib Mesylate twice a day and the dose will be escalated to 400 mg twice a day after 2 weeks in the same patient if no toxicity occurs. If grade 3/4 toxicity is observed, the dose of Imatinib Mesylate will be reduced as outlined in section 6.2 and 6.3 and the subsequent patients will be treated at that dose levels. The dose for Letrozole will be 2.5 mg, per oral, given once a day.

### **5.2 Phase II Part**

The dose for Imatinib Mesylate will 400 mg, twice a day (total daily dose 800 mg), per oral. Imatinib Mesylate is a local irritant and must be taken in a sitting position with a large (250 mL) glass of water. (Direction of use on medication label: Take as directed with a large glass of water). Imatinib Mesylate should not be taken with grapefruit juice.

The dose for Letrozole will be 2.5 mg, once a day, per oral.

### **5.3 Duration of Therapy**

In the absence of treatment delays due to adverse event(s), treatment may continue for 8 weeks or until one of the following criteria applies:

- Disease progression,
- Intercurrent illness that prevents further administration of treatment,
- Unacceptable adverse event(s),
- Patient decides to withdraw from the study, or
- General or specific changes in the patient's condition render the patient unacceptable for further treatment in the judgment of the investigator.

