# **7.0 Conduct of the Study**

## **7.1 Visit Schedule**

- 7.1.1 Baseline laboratory must be done within 14 days of study entry.
- 7.1.1 Baseline imaging studies must be done within 4 weeks of study entry.
- 7.1.3 Baseline imaging studies will include computed tomography of chest and abdomen and bone scan (correlating bone X-rays is required if bone scan is positive), or PET scan.
- 7.1.4 Baseline laboratory studies will include a complete blood count, electrolytes, liver functions, tumor markers (CEA and CA 27.29), creatinine.

7.1.5 Laboratory tests: Week 1 2, 3, 4, 6, 8: Complete blood count, liver, electrolytes and creatinin. These laboratory tests will be performed monthly thereafter.

7.1.6 Clinic visits with physical exam: Baseline, months 1, 2, 4, 6, 9, 12 (Tumor markers (CEA and CA 27.29) will be drawn during these visits.

7.1.7 Radiologic imaging/restaging: Months 2, 4, 6, 9, 12 : Affected area will be evaluated. Patients with stable or responsive disease will be followed every 3 months thereafter.

7.1.8 Correlative studies: Serum for angiogenic molecules and cytokines including: serum vascular endothelial growth factor (sVEGF), basic fibroblast growth factor (bFGF), Interleukine-8 (IL-8), platelet-derived growth factor (PDGF), E-selectin, tumor-necrosis factor- $\alpha$  (TNF- $\alpha$ ), tumor-necrosis factor- $\beta$  (TNF- $\beta$ ), IGF-II and IGFBP-3 and proteomic analysis: Baseline and months 2 and 4.

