**Table 7 Evaluation and Visit Schedule**

Examination	Prestudy	Week					Month				
		1	2	3	4	6	2	4	6	9	12
Informed consent	X										
Demographics	X										
Medical History	X										
Concurrent Medications	X				X		X	X	X	X	X
Inclusion/exclusion criteria	X										
Vital signs	X				X		X	X	X	X	X
Physical examination	X				X		X	X	X	X	X
Performans Status	X				X		X	X	X	X	X
Body Weight	X				X		X	X	X	X	X
Height	X										
ECG	X										
Laboratory test	X		X	X	X	X	X	X	X	X	X
Imaging studies	X						X	X	X	X	X
Serum markers	X						X	X			
Tissue markers	X						X				

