### 8.3 Response Definitions:

**Complete Response (CR).** Disappearance of all evidence of tumor for at least one cycle of therapy (four weeks). Bone lesions must have improved by scan and shown complete reossification by x-ray. The patient must be free of all symptoms of cancer. Markers must be normal.

**Partial Response (PR).** 30% or greater decrease in the sum of the products of diameters of all measured lesions persisting for at least one cycle of therapy or 4 weeks. Non-measurable, but evaluable, lesions must decrease by at least 30%. No lesion may increase in size and no new lesion may appear. Bone lesions must have improved by scan and shown some reossification by x-ray. Markers must have improved.

**Minor Response (MR).** A measurable decrease in measurable lesion(s), which is too small or too brief to qualify as a Partial Response. MR is considered a failure, but should be noted as a possible signal of biologic activity.

**Progressive Disease (PD).** Any increase of  $\geq 25\%$  in the sum of the products of diameters of any measurable lesion or in estimated size of non-measurable lesions or appearance of an unequivocally new lesion. Patients should have received at least two cycles of therapy before a designation of progression is made. An increase of 50% or development of unequivocally new lesions between the first and second cycle will be considered progression without repeat measurements.

**No Change (NC).** No change in tumor size, or  $<25\%$  increase in size.

MR and PD are considered failures.

Development of a new brain lesion will be considered progressive disease.

**Confirmation of Response.** To be assigned a status of PR or CR, changes in tumor measurements must be confirmed by repeat assessments that should be performed 4 weeks after the criteria for response are first met. In the case of SD, follow-up measurements must have met the SD criteria at least once after study entry at a minimum interval of 8 weeks.

**Response and Survival Durations.** The survival of patients will be measured from entry into protocol. Duration of response will be measured from first observation of the response until progression of disease.

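### Section 5.3 can be read as an 8-week limit on treatment, in conflict with section 4.2 and with the rest of the plan, which points to treatment until progression

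*Combined protocol and SAP*

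**What the plan says.** The treatment plan deals with duration in section 5.3. Provided that adverse events cause no delays, "treatment may continue for 8 weeks or until one of the following criteria applies". The criteria that follow are progression, intercurrent illness, unacceptable toxicity, patient withdrawal, and a change in condition that in the investigator's judgment rules out further treatment.

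Section 4.2 (Imatinib Mesylate) says that the drug is supplied "for an exposure period of up to 12 months or so long as the patient remains on study provided the patient shows continuous benefit", subject to there being no safety concerns. It then adds: "Continuing treatment beyond this period will be at the discretion of the investigator".

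The schedule in section 7.1 runs well past week 8. After weekly and fortnightly blood tests up to week 8, "These laboratory tests will be performed monthly thereafter". Imaging is set out as "Radiologic imaging/restaging: Months 2, 4, 6, 9, 12 : Affected area will be evaluated", and patients who are stable or responding are then followed every 3 months. Table 7 shows the same visits to month 12 and does not mark any of them as on or off treatment.

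Section 8.3 requires a response to be confirmed 4 weeks after its criteria are first met. Section 13.0 compares ORR with 136 responses in 453 patients on letrozole alone. Section 2.2.1 says that the patients in that trial were treated until progression or discontinuation for another reason.

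**The concern.** Section 5.3 is the clause a treating clinician would consult to decide when to stop. It names a fixed period and joins it to the stopping criteria with *or until*. One natural reading is that treatment ends at week 8 or at the first criterion, whichever comes sooner. The opening condition about delays favours that reading, because a delay matters to a duration only if there is a set course to complete. A clinician who relied on section 4.2 would instead keep a benefiting patient on imatinib for up to a year or longer. Two clinicians could treat identical responders differently and each cite the protocol.

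The primary endpoint and the interim stopping rule both rest on confirmed response. Under the 8-week reading, drug would be withdrawn from responders just when response is first imaged and before it can be confirmed. Section 1.0 also lists time to progression and survival on the combination as an objective, and nothing says what patients would receive after week 8.

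**Working it through.** The plan states no figure on this point. The check sets the clauses side by side and adds calendar arithmetic.

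**1. Where week 8 falls.** 8 × 7 = 56 days. Month 2 is 2 × 30.44 = 60.9 days. An 8-week limit therefore coincides, to within about 5 days, with the first post-baseline restaging in section 7.1.

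**2. When a month-2 response is confirmed.** Section 8.3 adds 4 weeks: 8 + 4 = week 12. That is 4 weeks after treatment would have ended. Superficial lesions followed by physical examination are an exception: a response seen at month 1 (week 4) could be confirmed at 4 + 4 = week 8.

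**3. Wording of the response definitions.** Complete response requires "Disappearance of all evidence of tumor for at least one cycle of therapy (four weeks"). If therapy has ended, it is unclear whether a complete response first seen at week 8 can satisfy this. Partial response is less exposed, because it need only be "persisting for at least one cycle of therapy or 4 weeks".

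**4. The progression rule.** Section 8.3 normally expects at least two cycles before progression is called: 2 × 4 = 8 weeks. Under an 8-week limit, the progression criterion in section 5.3 could act earlier only through the stated exception (a 50% increase, or an unequivocally new lesion, between the first and second cycles). It would otherwise have almost no role.

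**5. Reasons to stop elsewhere.** Section 9.0 gives ten reasons for discontinuing and section 11.0 gives the grounds for withdrawal. Neither includes completion of a fixed course.

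**6. The schedule.** Of the five restagings (months 2, 4, 6, 9, 12), four would fall after an 8-week limit. Monthly blood counts, liver tests, electrolytes and creatinine after week 8 make most sense for patients still on drug.

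**7. The benchmark.** 136/453 = 0.300, from a trial that treated until progression.

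**8. Whether section 13.0 depends on duration.** With X1 and X2 independent binomial(15, p), the probability of early termination is P(X1 ≤ 3) + Σ P(X1 = x) · P(X2 ≤ 7 − x), summed over x = 4 to 7.

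| True ORR | Stated | Exact |
|---|---|---|
| .20 | .83 | .819 |
| .30 | .40 | .393 |
| .35 | .22 | .220 |
| .40 | .11 | .108 |
| .45 | .05 | .048 |
| .50 | .02 | .019 |

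The posterior probability that ORR exceeds letrozole's by more than .10 is 0.043 at 3/15 and 0.122 at 4/15, and 0.026 at 7/30 and 0.059 at 8/30. Against the 0.05 cut-off this reproduces the boundaries of 4/15 and 8/30. The 90% credible interval at 18/45 has width 0.232, against the stated 0.24. Treatment duration is not an input to any of these, so the wording of section 5.3 does not change them.

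**The case against.** The strongest reply is that the duration is clear from the plan as a whole. Section 5.3 says *may*, and it does not say *maximum* or *whichever comes first*. Its *or* allows treatment until a criterion is met just as readily as treatment for 8 weeks. Steps 4 to 6 all fit treatment until progression, with 8 weeks perhaps intended as the minimum course before the first assessment. Section 4.2 is a supply clause, so its 12 months is a ceiling on what the manufacturer provides and does not set a required duration. Every harm described arises only if a site adopts the less favoured reading.

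Most of this stands. A reader might infer that section 5.3 plainly orders a stop at week 8, or that the documents leave the intended duration open. They do not support either inference: the text is ambiguous, and the surrounding sections lean one way. A reader might also infer that ORR will be biased downward by some amount, or that the design's operating characteristics are wrong. The documents give no basis for the first, and the check of section 13.0 shows no such problem for the second.

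The reply does not remove the ambiguity itself. The contrary evidence is spread over five other sections, and none of them overrides or explains the sentence that governs duration.

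**Conclusion.** The point holds as a fault in the wording of an operative treatment instruction. Section 5.3 admits an 8-week reading that conflicts with section 4.2 and sits badly with sections 7.1, 8.3, 9.0 and 11.0. Treatment until progression is the better inference.

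The practical consequences depend on a site actually applying the limit. In that case responders lose drug at month 2, an imaged month-2 response is confirmed about 4 weeks after the last dose, and the comparison with the letrozole benchmark is no longer matched on duration. How many responses would be lost cannot be calculated, because the documents give no data on when responses occur or how long they last off treatment. The calendar arithmetic assumes that month 2 is about week 8, and that confirmation takes place at the 4-week interval in section 8.3.

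**What to change.** Delete *for 8 weeks or* from section 5.3, so that treatment continues until one of the listed criteria applies. This brings the section into line with section 4.2 and with the schedule.

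The cost is one written amendment. Section 12.1 requires approval by the drug supplier and the investigator before implementation. IRB approval is also needed: section 12.1 asks for it when an amendment significantly affects safety, scope or scientific quality, and section 12.4 asks for it for any amendment that is not administrative. The change adds no visits, procedures, patients or analyses. The maximum of 45 patients, the boundaries of 4/15 and 8/30, and the termination table need no revision.
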